### **3.8.2 Secondary Endpoints**

#### **3.8.2.1 Duration of Response (DOR)**

The primary definition of DOR is the time from first documentation of response to the time of first documentation of deterioration from best response (e.g., CR to PR, or PR to LR).

The secondary definition of DOR is the time from first documentation of response to the time of first documentation of lack of response.

The tertiary definition of DOR is the time from first documentation of response to the time of initiation of new systemic cGVHD therapy (which will be defined by clinical team review).

The quaternary definition of DOR is the time from first documentation of response to the time of first documentation of lack of response (as the secondary definition) but with durations summed for multiple response/lack of response episodes.

The DOR will be reported only for responders and statistics will include:

- Kaplan-Meier plots and descriptive statistics of DOR. The censoring rules in [Table 2](#) will be applied
- Landmark analyses: Number and percentage of subjects with response sustained for  $\geq 12$ ,  $\geq 20$ ,  $\geq 24$ ,  $\geq 32$ ,  $\geq 36$ , and  $\geq 48$  weeks

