**Table 2. Censoring Rules for Duration of Response**

DOR	Events	Censoring
Primary	
 
• Deterioration from best response
 
• Initiation of new systemic therapy for cGVHD
 
• Death
 
	
 
• Last documented response assessment
 
• If LR or initiation of new systemic therapy happens immediately after two or more missed response assessments, the event date should be set as four weeks (one cycle) after last documented response assessment prior this event
 

Secondary	
 
• Documented LR
 
• Initiation of new systemic therapy for cGVHD
 
• Death
 
	
Tertiary	
 
• Initiation of new systemic therapy for cGVHD
 
• Death
 
	Last response assessment or long term follow up assessment, whichever is the latest and available
Quaternary	
 
• Documented LR
 
• Initiation of new systemic therapy for cGVHD
 
• Death
 
 
With summation of DOR from multiple episodes
	Same with censoring rule for primary and secondary

cGVHD = chronic graft versus host disease; DOR = duration of response; LR = lack of response

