### **3.14 Primary CSR Analysis**

A primary CSR analysis will be conducted 1 year after the last subject is enrolled.

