**Table 5. Efficacy TLFs**

T/F/L	Title	Population
Primary Endpoint: ORR		
T	Overall Response Rate	mITT
T	Best Overall Response	mITT
L	Listing of Overall Response by subject by visit	mITT
Secondary Endpoint: DOR		
T	Descriptive Kaplan-Meier and landmark statistics for primary DOR	Responder
F	Kaplan-Meier plot of primary DOR	Responder
L	Listing of all primary DOR episodes for each subject	Responder
T	Descriptive Kaplan-Meier and landmark statistics for secondary DOR	Responder
F	Kaplan-Meier plot of secondary DOR	Responder
L	Listing of all secondary DOR episodes for each subject	Responder
T	Descriptive Kaplan-Meier and landmark statistics for tertiary DOR	Responder
F	Kaplan-Meier plot of tertiary DOR	Responder
L	Listing of all tertiary DOR episodes for each subject	Responder
T	Descriptive Kaplan-Meier and landmark statistics for quaternary DOR	Responder
F	Kaplan-Meier plot of quaternary DOR	Responder
L	Listing of all quaternary DOR episodes for each subject	Responder
Secondary Endpoint: TTR		
T	Descriptive statistics for time to response (TTR) and cumulative response rate over time	Responder
L	Listing of TTR for each subject	Responder
Secondary Endpoint: Response by Organ System		
T	Best response by individual organ	mITT
T	Best response by individual organ	Responder
L	Listing of organ score and response assessment by subject and visit	mITT
T	Descriptive statistics for time to response (TTR) and cumulative response rate over time by organ	mITT
T	Descriptive statistics for time to response (TTR) and cumulative response rate over time by organ	Responder
Secondary Endpoint: TTNT		
T	Descriptive Kaplan-Meier and landmark statistics for TTNT	mITT
F	Kaplan-Meier plot for TTNT	mITT
Secondary Endpoint: Corticosteroid Dose		
T	Descriptive statistics for prednisone equivalent dose of corticosteroids	mITT Responder

T/F/L	Title	Population
		Non-responder BL corticosteroid dose level (upper and lower 50 th percentiles)
T	Summary of raw and change from baseline on prednisone equivalent dose of corticosteroids by visit	mITT Responder Non-responder BL corticosteroid dose level (upper and lower 50 th percentiles)
L	Listing of all the steroid raw and standardized dosing by subject and visit	mITT
Secondary Endpoint: CNI Dose		
T	Summary of descriptive statistics for CNI	mITT
L	Listing of all the CNI dosing by subject and visit	mITT
Secondary Endpoint: FFS		

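### Quaternary DOR: Kaplan-Meier on summed response episodes gives an estimate that depends on length of follow-up as well as on the drug, and Table 2 does not fix the status of a summed time

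*SAP*

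**What the plan says.** SAP 3.8.2.1 gives four definitions of DOR. The fourth takes the secondary definition (first response to first LR) "but with durations summed for multiple response/lack of response episodes". For DOR in general the section plans "Kaplan-Meier plots and descriptive statistics of DOR", and landmarks worded as "Number and percentage of subjects with response sustained for" at least 12 up to at least 48 weeks.

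Table 2 lists three events for the quaternary version: documented LR, new systemic cGVHD therapy, and death. It adds "With summation of DOR from multiple episodes". The censoring cell reads only "Same with censoring rule for primary and secondary".

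Table 5 commits to "Descriptive Kaplan-Meier and landmark statistics for quaternary DOR" and a "Kaplan-Meier plot of quaternary DOR", both in responders. SAP section 4 presents results by cohort and overall.

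On timing, SAP 2.2 enrols the cohorts in sequence, each waiting for 8 subjects of the previous cohort to reach 2 months. SAP 3.14 sets one cut: "A primary CSR analysis will be conducted 1 year after the last subject is enrolled".

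**The concern.** Kaplan-Meier needs an event that ends the clock and censoring that says nothing about the remaining time. The summed clock fails on both counts.

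- **LR does not end the clock.** It includes unchanged and mixed status (SAP 3.8.1). Subjects with stable disease continue dosing (Protocol Table 1, note o), and mixed responders may continue with medical monitor approval (Protocol 6.3). A definition that sums episodes presupposes that response can be regained.
- **Censoring is informative.** Two subjects with equal calendar follow-up are censored at different summed times, according to how much of that follow-up each spent in response.
- **Status is undefined.** Table 2 counts LR as an event and also sums past it. It does not say whether a subject who lost and regained response is an event or is censored at the total.

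An invented subject shows the effect. Take 12 weeks of response, 8 weeks of LR, 12 more weeks of response, then LR, with the last state deciding the status. A cut at week 16 after first response gives an event at 12 weeks. A cut at week 24 gives a censored time of 12 + 4 = 16 weeks. A cut at week 36 gives an event at 12 + 12 = 24 weeks. An ordinary survival event, once recorded, does not undo itself.

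At stake is a by-cohort display of durability in which part of any difference may come from the calendar.

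**Working it through.** The plan states no expected value for this quantity, so there is no figure to reproduce. The check is a simulation. Its rates are assumptions, because the documents give none.

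**Inputs from the documents**
- Cycle and assessment interval: 4 weeks.
- Shortest follow-up after first response for an early responder in the last cohort: about 52 weeks to the cut, less 4 weeks to Cycle 2 Day 1, is 48 weeks.
- Minimum gap from Cohort 1 to Cohort 3: two steps of about 2 months, or about 2 x 8 = 16 weeks. This gives 48 + 16 = 64 weeks for Cohort 1. Actual accrual is not stated, so 96 weeks is shown as a wider contrast.

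**Assumed per cycle:** response to LR 10%, LR back to response 12%, new therapy or death 2% from either state. The process is the same at every follow-up length, with at least 20,000 simulated responders for each.

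**Check on the secondary DOR.** A first episode ends with probability 0.10 + 0.02 = 0.12 per cycle. Since 0.88^5 = 0.53 and 0.88^6 = 0.46, the median is 6 cycles, or 24 weeks. The share reaching at least 48 weeks is 0.88^11 = 0.245. The simulation returns 24 weeks and about 0.25 at every follow-up length.

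**Quaternary DOR, LR at the cut counted as an event**

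| Follow-up after first response | KM median | KM at 48 weeks |
|---|---|---|
| 48 weeks | 40 weeks | 0.42 |
| 64 weeks | 44 weeks | 0.50 |
| 96 weeks | 56 weeks | 0.59 |
| Very long | 80 weeks | 0.68 |

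The crude share with at least 48 summed weeks, which is how the landmark wording reads, goes from 25% at 48 weeks of follow-up to 54% at 96 weeks.

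**Sensitivity to what happens after LR** (loss 10% and exit from response 2% kept; LR as an event; 48 versus 96 weeks of follow-up)

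| Exit from LR | Regain | KM median, weeks | KM at 48 weeks |
|---|---|---|---|
| 2% | 12% | 40 vs 56 | 0.42 vs 0.59 |
| 10% | 12% | 36 vs 40 to 44 | 0.38 vs 0.46 |
| 20% | 12% | 32 vs 36 | 0.35 vs 0.39 |
| 20% | 5% | 28 vs 28 | 0.29 vs 0.31 |
| any | 0% | equals the secondary DOR | no dependence |

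(In the second row the curve sits close to one half between 40 and 44 weeks, so the median varies by one step between runs.)

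**Only new therapy or death counted as an event.** With the base rates, the 48-week estimate falls from 0.74 at 48 weeks of follow-up to 0.68 at very long follow-up. Shorter follow-up now looks better.

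**Response to the drug at fixed follow-up.** With 18 to 21 cycles, regain 25%, exit from LR 10%, exit from response 1% and LR as an event, loss rates of 25%, 15%, 8% and 4% per cycle give medians of 32, 48 and 72 weeks and not reached.

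**The case against.** The case on the other side has real force.

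- **Re-response may be uncommon on record.** LR includes progression, which ends dosing, and response is scheduled for assessment only through end of treatment (Protocol 10.1). Later contact covers survival and treatment changes (Protocol 8.8). If most LR subjects leave treatment, the shift is small, as the fourth row of the sensitivity table shows. This stands and limits the size. It does not rescue the method wherever response is regained, which is the only case in which this definition differs from the secondary one.
- **Little rests on it.** It is one of four descriptive definitions, with no between-cohort test planned. At the 25% response rate assumed in Protocol 17.2, 16 subjects give 16 x 0.25 = 4 responders per cohort. The simulated sampling SD of the 48-week estimate is then about 0.25 to 0.28, larger than the shift. This also stands.
- **A regulator was involved.** The SAP document history says that DOR definitions were added after an FDA meeting. The documents do not show what was agreed, which is a reason to keep the definition itself.

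Two stronger readings are tempting. A reader might infer that the estimate reflects follow-up instead of the drug. It does not: at fixed follow-up it responds strongly to loss and regain, and its growth with follow-up levels off. A reader might also infer that Cohort 1 is bound to look better. The documents do not settle that, because the direction depends on a status rule that Table 2 leaves open.

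**Conclusion.** The concern holds in this form. Kaplan-Meier and landmark percentages do not suit a summed time whose listed event does not end the clock, and Table 2 leaves the status of that time undefined. Both status rules in the working make the estimate depend on follow-up when response can be regained. With LR as an event, the natural reading of Table 2, earlier cohorts gain; with only new therapy or death as events, later cohorts gain.

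On the LR-as-event reading and the base rates, the documented minimum gap moves the median by 4 weeks and the 48-week estimate by 0.50 - 0.42 = 0.08. A gap of 48 weeks moves them by 16 weeks and 0.17. The effect is close to nil with 20% exit from LR and 5% regain, and zero with no regain. All sizes rest on assumed rates and on accrual that the documents do not give. Severity is low to moderate.

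**What to change.** In SAP 3.8.2.1, Table 2 and Table 5:

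1. Keep the quaternary definition and its episode listing.
2. Replace its Kaplan-Meier curve, median and landmark percentages with total weeks in response within a common window from first dose that every subject can complete at the cut. Either 48 or 52 weeks would serve; 48 is safer if first dose can fall after enrolment. Report the mean with a 95% CI by cohort, for responders and for the mITT population with non-responders at 0.
3. State the counting rule in Table 2: each episode runs from the visit documenting response to the visit documenting LR, and counting stops at new systemic therapy, death or the last documented response assessment. Unassessed time after end of treatment is then not credited as response.

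The cost is SAP wording and one replacement table. This definition loses its median and curve; the other three keep theirs. Subjects who stop KD025 while still responding are credited only up to their last assessment, which is conservative and should be noted in the table. With about 4 responders per cohort the intervals will be wide. If the Kaplan-Meier display itself was agreed with the regulator, the change would also need to be communicated.

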10. ACTIVITY

The primary activity endpoint of this study is subject response based on the 2014 NIH Consensus Development Project on Clinical Trials in cGVHD. Secondary endpoints include evaluation of cGVHD severity using the Physician-reported global cGVHD Activity Assessment; evaluation of symptom burden using the cGVHD Activity Assessment - Patient Self Report; FFS; OS; TTNT; changes in corticosteroid and CNI dose; and changes in symptom burden/bother using the Lee cGVHD Symptom Scale.

10.1. 2014 NIH Consensus Development Project on Clinical Trials in cGVHD

Subject response (CR, PR, or LOR [unchanged, mixed response, progression]) based on the 2014 NIH Consensus Development Project on Clinical Trials in cGVHD is the primary activity endpoint for this study (see [Appendix B](#)). Response criteria will be assessed on Day 1 of each cycle starting on Cycle 2 Day 1 as well as the EOT visit.

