## **2.2 Study Design**

This is a Phase 2a, open-label, dose-escalation, safety, tolerability, and activity study.

Subjects who have signed an Institutional Review Board/Independent Ethics Committee-approved informed consent form and who have met all of the inclusion/exclusion criteria will be enrolled. After approximately 4 weeks for screening, subjects will receive KD025 orally (PO) in 28-day cycles until disease progression or unacceptable toxicity occurs followed by 4 weeks of follow-up. In addition, subjects will be contacted every 8 weeks until study close-out to confirm survival status and the initiation of any anticancer treatment or any changes in treatment for cGVHD.

Sequential cohorts of approximately 16 subjects will be dosed at KD025 200 mg once daily (QD) PO, KD025 200 mg twice daily (BID) PO, and KD025 400 mg QD (Table 1). Prior to enrolling subsequent cohorts, the safety data in each previous cohort will be evaluated after 8 subjects have reached 2 months of treatment.

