### **3.1.2 General Considerations**

General considerations for descriptive statistics and presentation for continuous and categorical data are given below.

Continuous data will be described using descriptive statistics: number of observations (n), mean, standard deviation, median, minimum, and maximum. Frequencies and percentages will be used for summarizing discrete (categorical) data. When categorical data are presented, the percent will be suppressed when the count is zero in order to draw attention to the nonzero counts. The denominator for all percentages, unless otherwise specified, will be the number of subjects in the cohort or in the specified analysis population.

Means, medians, standard deviations, and confidence intervals (CIs) will be reported to one decimal place more than the data reported on the case report form (CRF) or by the vendor. Minimum and maximum will be reported to the same number of decimal places displayed on the CRF or by the vendor. P-values will be reported to 4 decimal places.

Unless otherwise indicated, all summary tables will be presented by the following groups: Cohort 1 (KD025 200 mg QD PO), Cohort 2 (KD025 200 mg BID PO), Cohort 3 (KD025 400 mg QD PO), and Overall.

Because of the exploratory nature of the study, no adjustments will be made for the multiplicity of endpoints.

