T	Descriptive Kaplan-Meier and landmark statistics for FFS (with cumulative failure rates for each of the 3 components FFS)	mITT
F	Kaplan-Meier plot for FFS (with cumulative failure rates for 3 components of failures)	mITT
L	Listing of failure events	mITT
Secondary Endpoint: Change in cGVHD severity as based on the Clinician-reported Global cGVHD Activity Assessment		
T	Maximal change from baseline in global severity rating based on Clinician-reported cGVHD Assessment	mITT
Secondary Endpoint: Symptom activity using the cGVHD Activity Assessment Patient Self-Report		
T	Maximal change from baseline in symptom activity (scored 0-10) based on cGVHD Activity Assessment Patient Self Report	mITT
T	Summary of severity rating on categorical status (none, mild, moderate, severe) based on cGVHD Activity Assessment Patient Self Report by visit	mITT
T	Descriptive statistics of cGVHD symptoms based on cGVHD Activity Assessment Patient Self Report (change of cGVHD symptom to a month ago) by visit	mITT
Secondary Endpoint: LSS score		

T/F/L	Title	Population
T	Descriptive statistics for LSS score	mITT Responder Non-responder
T	Summary of LSS Score (overall and each of seven domains) raw and change from baseline by visit	mITT Responder Non-responder
L	Listing of Lee Symptom Scale Score by subject, domain and visit	mITT
Subgroup analyses (subgroups are listed in section 3.8.4 Subgroup Analyses )		
T	Overall Response Rate by Subgroup	mITT
T	Descriptive Kaplan-Meier and landmark statistics for primary DOR by subgroup	mITT
F	Kaplan-Meier plot of all DOR by subgroup	mITT
L	Listing of PPI patients by cohort	mITT

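### The DOR landmarks are planned as simple percentages with no rule for responders censored before the landmark, which lowers chiefly the ≥48-week figure in the last-enrolled dose cohort

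*SAP*

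**What the plan says.** SAP 3.8.2.1 states that "The DOR will be reported only for responders and statistics will include" two items. The first is Kaplan-Meier plots and descriptive statistics, to which the Table 2 censoring rules are attached. The second is "Landmark analyses: Number and percentage of subjects with response sustained for" at least 12, 20, 24, 32, 36 and 48 weeks. No censoring rule is attached to the second item.

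Two general rules could decide how a censored responder enters that percentage:

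- SAP 3.1.2: "The denominator for all percentages, unless otherwise specified, will be the number of subjects in the cohort or in the specified analysis population".
- SAP 3.1.5: for categorical variables, subjects with missing data are left out of percentages unless specified otherwise. It does not say whether a censored duration is missing data.

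Four other provisions matter:

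- **Data cut (SAP 3.14):** "A primary CSR analysis will be conducted 1 year after the last subject is enrolled".
- **Assessments (Protocol 10.1):** "Response criteria will be assessed on Day 1 of each cycle starting on Cycle 2 Day 1 as well as the EOT visit".
- **Enrolment (SAP 2.2):** cohorts are sequential, and safety in each cohort "will be evaluated after 8 subjects have reached 2 months of treatment" before the next one opens.
- **Outputs (SAP Table 5):** "Descriptive Kaplan-Meier and landmark statistics for primary DOR" is listed for the Responder population, but "Descriptive Kaplan-Meier and landmark statistics for primary DOR by subgroup" and the matching subgroup plot are listed for mITT.

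**The concern.** A percentage with response sustained for at least L weeks estimates durability only if every responder in the denominator could have been observed for L weeks after first response. Here, some could not. The late enrollers are all in Cohort 3 (400 mg QD), because the cohorts were filled in order.

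If a responder still in response at the data cut counts as not sustained, equal durability at all three doses gives a lower ≥48-week percentage in Cohort 3. Summaries are by cohort, so a reader could take this for a dose effect. The Kaplan-Meier statistics in the same table would give a different 48-week figure, with nothing to explain the gap.

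**Working it through.** The documents state no DOR landmark figure, so there is none to reproduce.

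**1. Follow-up implied by the documents.** Response is first assessable at week 4, then every 4 weeks. One year is about 52 weeks.

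- Last-enrolled subject, first response at week 4: 52 − 4 = 48 weeks observable. This has no slack, because Cycle 14 Day 1 is day 13 × 28 + 1 = 365.
- Same subject, first response at week 8: 52 − 8 = 44 weeks, so 48 is out of reach.
- First eight Cohort 1 subjects: two safety gates of 2 months (8.7 weeks each) precede Cohort 3, so follow-up is at least 52.2 + 2 × 8.7 = 69.6 weeks. Since 69.6 − 48 = 21.6, a first response as late as the week-20 assessment can still reach 48 weeks.

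**2. Formula.** If follow-up F is independent of DOR, on the default denominator:

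crude(L) = P(DOR ≥ L) × M(L), where M(L) = Σ p_w × P(F ≥ w + L)

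Here p_w is the share of responders whose first response is at week w.

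**3. Assumptions (none is in the documents).** First response at weeks 4/8/12/16/24 in 40/30/15/10/5%. Even enrolment, with each cohort taking 26 or 16 weeks and the next opening when it is full and the gate is met. Exponential DOR, failures found at 4-weekly assessments, administrative censoring only. Cohort 3 is then followed for 52–78 or 52–68 weeks.

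**4. Cohort 3 multiplier at 48 weeks.** For example, P(F ≥ 56) = (78 − 56)/26 = 0.846.

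- 26-week accrual: 0.40×1 + 0.30×0.846 + 0.15×0.692 + 0.10×0.538 + 0.05×0.231 = 0.823
- 16-week accrual: 0.40×1 + 0.30×0.75 + 0.15×0.50 + 0.10×0.25 + 0.05×0 = 0.725

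Cohort 1 is 1.00 in both cases; Cohort 2 is 1.00 or 0.99. For the other Cohort 3 landmarks the multiplier is 1.00 at 12, 20 and 24 weeks, 0.99 at 32 and 0.985 or 0.975 at 36.

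**5. Cohort 3, ≥48 weeks.** A duration of at least 48 weeks requires no failure by week 44, so P(DOR ≥ 48) = 2^(−44/48) = 0.530 for a median of 48 weeks and 2^(−44/24) = 0.281 for 24. The crude figure at median 48 is 0.530 × 0.823 = 0.436 or 0.530 × 0.725 = 0.384.

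If censored responders are excluded, the figure is sustained / (sustained + observed failures). The observed-failure shares come from simulation under the same assumptions: 0.436/(0.436 + 0.465) = 0.484 and 0.384/(0.384 + 0.463) = 0.453. Exclusion is still biased low, because early failures are seen while long responses are removed.

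| Median DOR | True (Kaplan-Meier target) | Default denominator, 26 / 16 weeks | Censored excluded, 26 / 16 weeks |
|---|---|---|---|
| 48 weeks | 53% | 44% / 38% | 48% / 45% |
| 24 weeks | 28% | 23% / 20% | 24% / 22% |

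**6. A cut 8 weeks later.** Cohort 3 follow-up becomes 60–86 or 60–76 weeks.

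- 26-week accrual: 0.40 + 0.30 + 0.15 + 0.10×0.846 + 0.05×0.538 = 0.96, so crude is 51% against 53%.
- 16-week accrual: 0.40 + 0.30 + 0.15 + 0.10×0.75 + 0.05×0.25 = 0.94, so crude is 50%.

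**7. Wider assumptions.** With accrual of 8 to 39 weeks per cohort, earlier or later response times, median DOR of 26 or 52 weeks and no drop-out, the Cohort 3 ≥48-week shortfall runs from 1.9 points (25.9% against 27.8%) to 29.6 points (23.1% against 52.7%).

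**8. Scale.** At the planning response rate (Protocol 17.2), 16 × 25% = 4 responders per cohort. At median 48 the mean Cohort 3 loss is 4 × (0.530 − 0.436) = 0.38 or 4 × (0.530 − 0.384) = 0.58 of a responder. One censored responder moves the cohort figure by 1/4 = 25 points and the overall figure by 1/12 = 8 points. Over both medians and both accrual rates, at least one of the four is censored before 48 weeks in 21–49% of simulated trials.

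**The case against.** The strongest reply is that the plan already has an estimate that handles censoring. Kaplan-Meier statistics stand in the same table for every DOR definition. An observed count of responses lasting 48 weeks is a legitimate description, no test or decision rule uses the landmarks, and under administrative censoring one landmark of six in one cohort of three is materially affected. All of this stands, and it limits the weight of the point. It does not remove it, because the printed percentage would differ from the Kaplan-Meier figure with no stated reason.

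A reader might infer that the SAP declares censored responders to be failures. It does not. That is the default reading of 3.1.2, and 3.1.5 could be read as excluding them. Both readings give a figure that is too low, the second by less.

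The hard 52-week cut can also be questioned. The summary of changes for Protocol Amendment 7 (23 October 2019) says the last subjects had enrolled more than a year before, while the SAP was still being updated. A later cut is therefore possible, and 8 weeks would remove most of the bias. SAP 3.14 still says 1 year, and the documents give no cut-off date.

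Finally, Kaplan-Meier is no clean remedy for the quaternary definition, which sums several episodes. On summed time the censoring is informative, because how much time a subject has accumulated by the cut depends on that subject's own pattern of response and loss. This objection is correct, and the fix allows for it.

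**Conclusion.** The concern holds as a reporting weakness of minor to moderate weight. The landmark percentages have no stated rule for censored responders, and either general rule biases Cohort 3 at ≥48 weeks downward. In the illustration with a median DOR of 48 weeks, 53% becomes 38–44% or 45–48%, and about 50–51% on the default denominator with a cut 8 weeks later. These figures rest on assumed accrual, response times and DOR.

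Two stronger inferences are not supported. One is that all landmarks are materially biased. Administrative censoring leaves 12 to 24 weeks unchanged and 32 and 36 weeks almost unchanged in the main illustration. Responders whose assessments stop while they are still responding would lower every landmark in every cohort, but the documents give no rate for this. The other is that the DOR analysis as a whole ignores censoring, which the Kaplan-Meier output contradicts.

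The population label is a plain inconsistency that needs no assumption. DOR is defined only for responders, yet the subgroup DOR outputs are labelled mITT. How Table 2 dates a death long after the last response assessment is a separate minor matter.

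**What to change.** - **SAP 3.8.2.1, primary, secondary and tertiary DOR:** report the landmark proportions as Kaplan-Meier estimates under the Table 2 rules, with 95% confidence intervals and numbers at risk, by cohort and overall. Read the curve just before each landmark, so that an event dated exactly then counts as sustained. Mark the estimate not estimable where the curve ends in censoring before the landmark.
- **Observed counts, if kept, and for quaternary DOR:** use responders as the denominator and show the numbers sustained, failed and censored before each landmark.
- **SAP Table 5:** change the population of the subgroup DOR table and plot from mITT to Responder.

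The cost is SAP wording and programming, with no new data. The downside is precision. With about 4 responders per cohort the 48-week Kaplan-Meier estimate has a standard deviation of about 24–26 points, and in Cohort 3 it was not estimable in 5–13% of simulated trials. It also assumes that censored responders resemble those still followed. That is reasonable for administrative censoring but less certain for subjects who stop study drug while responding.
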